## **1. BACKGROUND AND RATIONALE**

Varicose veins of the lower limbs affect many people worldwide with incident reports of its extent in 40% of women and 20% of men. Varicose veins occur as a result of weakening valves in veins, causing reversal of blood flow and venous reflux. Risk factors for varicose veins includes family history, obesity, prolonged standing, gender and number of offspring. Symptomatic presentation of varicose veins varies from itching, hyperpigmentation to phlebotic lymphedema, chronic swelling of legs, lipodermatosclerosis, and venous ulcerations. Current treatment options include vein stripping, thermal ablation therapy, such as endovenous laser ablation and non-thermal methods such as Venaseal and Clarivein. The goal of these treatments is to eliminate sources of reflux in order to control the progression of the disease, prevent recurrence and provide symptomatic relieve.

However, given the invasive and surgical nature of these current therapies, some patients do not undergo treatment in fear of the potential surgical complications and prolonged recovery periods. These invasive procedures are also associated with risks of infections and low cost-effectiveness. As such, novel non-invasive therapies are being researched and developed to better meet the need of patients with varicose veins.

More recently, echotherapy technology such as Sonovein®, a high intensity focused ultrasound (HIFU) treatment, has been introduced as a non-invasive alternative for the treatment of varicose veins. During echotherapy treatment, non-invasive high intensity ultrasound beam is focused on the troubled vein, delivering thermal energy. The vein then absorbs the thermal energy, shrinks, and is sealed. The non-invasive nature of echotherapy has the capacity to prevent infections, leaves no scars and discolouration, and removes the need for tumescence anaesthesia. Recovery period from echotherapy is also immediate and caters to all vein types. Further, the administration of echotherapy does not require the presence of external nurses, additional materials such as micro puncture kits, recovery or sterile rooms, making it a more cost-effective treatment compared to current invasive standards of care.

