### **3. EXPECTED RISKS AND BENEFITS**

No additional risk for study patients because they would undergo HIFU as per the assessment by their primary physicians as suitable treatment for the patients. There will not be any study specific interventions for the patients. For this study, we are administering Quality of Life questionnaires, as well as reviewing medical history and procedural information. There will be additional follow-ups arising from participation. There will be a slight inconvenience of multiple returns to clinic and taking time for questionnaires, minimal risk for breach of confidentiality. However, in terms of standard care, this is above and beyond what is expected.

Subjects stand to benefit from the closer monitoring post-procedure. In the long run, the medical knowledge gain with regards to treatment outcomes is beneficial for future patients.

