#### 5. STUDY DESIGN AND PROCEDURES/METHODOLOGY

The study involves prospective data collection of 30 patients that will be undergoing HIFU as choice of treatment for their varicose veins / CVI. Questionnaires will be conducted at 5 timepoints – baseline before procedure, 2 weeks, 3 months, 6 months and 12 months. Subjects will be seen at outpatient clinic post-procedure. Besides questionnaires, physical examination and duplex ultrasound scan will be conducted at 2 weeks, 3 months, 6 months and 12 months to ensure occlusion of treated vein.

3, 6 and 12 months: follow-up in clinic with VCSS, AVVQ, CIVIQ and EQ-5D as well as targeted duplex scan to look for anatomical recurrence

Analysis of results and cost evaluation

Physical Examination includes the assessment of:-

- GSV/SSV/AASV reflux
- CEAP Classification (Clinical, Aetiological, Anatomical and Pathophysiology)
- Venous Clinical Severity Score (VCSS)

Duplex ultrasound will be performed by vascular sonographers / vascular consultants. Reflux is determined at the sapheno-femoral (SF) / sapheno-popliteal (SP) junction in the lying and standing position using the Valsalva manoeuvre or manual distal compression with rapid release respectively. Reflux as documented by ultrasound is defined and considered significant as retrograde flow of >0.5 seconds.

Quality of Life questionnaires include:-

- ED5Q
- CIVIQ-14
- AVVQ (Aberdeen Varicose Vein Questionnaire)
- Pain Diary
- Patient Satisfaction Survey

Sonovein® is a unique echotherapy solution, combining therapeutic ultrasound and ultrasound for monitoring. The high-intensity ultrasound beam is focused on the vein through a magnifying glass. As thermal energy is delivered, the thermocoagulation property of ultrasound energy affects the vein wall, causing shrinking and collapsing of the target vein. Thus creating a fibrotic seal and occluding the vessel. The treated vein is immediately closed after the procedure, and its diameter will continuously reduce over time, becoming a fibrotic chord. The treatment along the vein is steered automatically via a touch screen monitor. In-beam linear ultrasound probe allows visualisation of the vein in real-time and insures optimal accuracy.

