### **11.1. Informed Consent**

PIs/Co-Is/Authorised Study Team Members will recruit eligible patients that are admitted / on follow-up with the Department of Vascular Surgery, Singapore General Hospital for varicose veins / chronic venous insufficiency. Prior to procedure, patients will first be screened and given enough time to consider participation. They will be briefed on what the study involves, as well as any risks/benefits involved. If they decide to participate, informed consent will be taken by PI/Co-I/authorised study team members.

Patients will be assured that the standard of care will not be affected, regardless of participation in study.

If there are non-English speaking patients, the study will be explained in their preferred language through a translator.

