#### **14. FUNDING and INSURANCE**

There will not be any funding required for this study. However, as goodwill, Theraclion (owner of Sonovein®) will be providing the consumables free of charge for study patients only.

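### Does the free supply of HIFU consumables to study patients bias the cost evaluation mentioned in Section 5?

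*Protocol*

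**What the plan says.** Four places in the protocol bear on the point.

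- **Section 5** contains the verbless line "Analysis of results and cost evaluation". It names no perspective, cost items, price source, comparator or time horizon. The same section describes a single group, namely "patients that will be undergoing HIFU as choice of treatment for their varicose veins / CVI".
- **Section 14** states "There will not be any funding required for this study" and adds that the owner of the device "will be providing the consumables free of charge for study patients only".
- **Section 1** asserts that HIFU needs fewer staff, materials and rooms than invasive treatment, "making it a more cost-effective treatment compared to current invasive standards of care".
- **Sections 3 and 11.1** describe what participation changes. Section 3 says "There will be additional follow-ups arising from participation" and, of this extra burden, "However, in terms of standard care, this is above and beyond what is expected". Section 11.1 says "Patients will be assured that the standard of care will not be affected, regardless of participation in study".

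Cost does not appear in the objective (Section 2). Section 8.2 covers closure, quality of life and functional results only.

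**The concern.** Two facts stand in the protocol and nothing connects them: a cost evaluation is foreseen, and one real input to HIFU is free, but only inside the study. A costing that records what was actually spent on these patients would leave that input out. The error would run in the manufacturer's favour, and towards a conclusion that Section 1 already states.

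Two further worries follow. Free supply might draw patients towards HIFU within the study, or lift the satisfaction scores that Section 2 places under the primary objective. It might also seem to contradict Section 3, where patients are to have HIFU on their physicians' assessment anyway, and the assurance in Section 11.1. If all this held, a published cost figure would not carry over to patients treated outside the study.

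**Working it through.** **Inputs.** The protocol has no unit price, no cost total and no consumable share, so there is no figure of its own to reproduce. The shares below are assumptions.

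**Step 1: procedure cost.** Let C be the true HIFU cost per patient and s the consumables' share of it.

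- Consumables entered at zero: observed cost = (1 − s) × C, so the understatement is s.
- Consumables entered at the outside price: observed cost = (1 − s) × C + s × C = C, so the understatement is 0.

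| Assumed s | Observed / true, valued at zero | Understatement at zero | Understatement at outside price |
|---|---|---|---|
| 20% | 0.80 | 20% | 0% |
| 40% | 0.60 | 40% | 0% |
| 60% | 0.40 | 60% | 0% |

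The third column repeats the first. The calculation shows how the bias would arise but gives no evidence of its size. The bias depends wholly on the valuation rule, and no section fixes that rule at zero.

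**Step 2: total cost.** Section 3 says that follow-up exceeds standard care. Let v be the cost of the extra visits as a fraction of C. If everything done in the study is counted and consumables are entered at zero, observed cost = (1 − s + v) × C. This is below C if v < s, equal to C if v = s, and above C if v > s. With s = 20%, for example, extra visits worth 20% of C would cancel the omission. The documents give neither quantity, so the sign of the net error in total cost is not established.

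**Step 3: is there a comparison to bias?** Every patient receives HIFU, and the comparisons in Section 8.2 are against each patient's own baseline in quality of life and function. A one-arm cost figure cannot by itself support the comparative statement in Section 1, which is argued from staff, kits and rooms and not from study expenditure. A misleading comparison would need outside cost data that the protocol does not plan to use.

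**Step 4: Sections 3 and 11.1 against Section 14.** The sentence in Section 3 explains why the study adds no risk. The sentence in Section 11.1 promises that the standard of care does not depend on taking part. Neither says anything about who pays. Free consumables contradict neither.

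**Step 5: selection and satisfaction.** Section 4.2 describes candidates as having already chosen HIFU when they are screened, which weakens the idea that the subsidy drives the choice. No section says that the patient, and not the hospital or an insurer, would otherwise bear the consumable cost. An effect on satisfaction is possible, but nothing in the protocol supports it.

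Sections 4.1 and 8.1 give 15 patients and Section 5 gives 30. That discrepancy does not affect this point, because the share is per patient.

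**The case for a change.** The strongest case for acting is that the protocol promises an output and gives it no basis. The assessments listed in Section 5 include no resource-use item, Section 8.2 has no cost analysis, and the one known distortion favours the company donating the goods. Section 1 counts the materials that competing procedures need, while HIFU's own materials are donated. The extra visits do not repair the missing consumable cost; they are a second study artefact that needs a rule of its own. Section 4.2 also has patients briefed on the study at the same time as the alternatives are explained, so the subsidy could enter the decision. Section 3 names closer monitoring as the benefit to subjects and does not mention the free supply. A few sentences would settle all of this.

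Part of this stands. The protocol does not say how donated consumables would be valued, and entering them at zero would understate the procedure cost. Anyone reporting a cost from this study should disclose the donation, separate study-driven visits from routine care, and refrain from a cost-effectiveness claim without a comparator. But these are matters of costing method and reporting. Silence on them in a protocol is not a wrong rule, and they can properly be set in an analysis plan. The line in Section 5 also follows another verbless line about follow-up, which suggests the last box of a flow chart and not a specified analysis. That reading is an inference. The effects on choice and satisfaction remain conjecture.

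**Conclusion.** No change to the protocol follows. This is a gap that a competent analyst fills sensibly, on an item that is not an objective, an endpoint or a planned comparison in a single-arm pilot. The understatement is conditional: equal to the consumables' share if they are costed at zero, nil if they are costed at the price payable outside the study. The documents give neither the share nor the rule, and the net direction for total cost is open because of the extra follow-up. The closure and quality-of-life analyses in Section 8.2 use no cost data and are untouched.

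The conclusion assumes that any cost result is descriptive and that the donated items are given a real price. If a later report set costs with zero-priced consumables against outside figures for invasive treatment, the criticism would apply to that report.

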## **6. SAFETY MEASUREMENTS**

### **6.1. Definitions**

Serious adverse event (SAE) in relation to human biomedical research, means any untoward medical occurrence as a result of any human biomedical research which:

- results in or contributes to death
- is life-threatening
- requires in-patient hospitalisation or prolongation of existing hospitalisation
- results in or contributes to persistent or significant disability/incapacity or
- results in or contributes to a congenital anomaly/birth defect
- results in such other events as may be prescribed

Adverse event (AE) in relation to human biomedical research means any untoward medical occurrence as a result of any human biomedical research which is NOT serious. Adverse event can be any unfavourable and unintended sign (including an abnormal laboratory finding), symptom, or disease possibly/ probably/ definitely associated with the participant in the human biomedical research.

### **6.2. Collecting, Recording and Reporting of Serious Adverse Events to CIRB**

Only related SAEs (definitely/ probably/ possibly) will be reported to CIRB. Related means there is a reasonable possibility that the event may have been caused by participation in the clinical trial. Please refer to the CIRB website for more information on Reporting Requirement and Timeline for Serious Adverse Events.

The investigator is responsible for informing CIRB after first knowledge that the case qualifies for reporting. Follow-up information will be actively sought and submitted as it becomes available.

Related AEs will not be reported to CIRB. However, the investigator is responsible to keep record of such AEs cases at the Study Site File.

### **6.3. Safety Monitoring Plan**

All patient data will be anonymised and stored on a password protected database under the guidelines of Personal Data Protection Act (PDPA). Patient data will also be kept on paper in the form of data collection forms (questionnaires etc.). These will be kept in a locked filing cabinet and stored in SGH for 10 years in accordance with local policy.

### **6.4. Complaint Handling**

Complaints will be addressed by the Principal Investigator, who will speak to the parties involved and identify the areas of discontent.

## **7. DATA ANALYSIS**

### **7.1. Data Quality Assurance**

Accuracy and completion of data collection will be the responsibility of PI and research co-ordinator. Research co-ordinator will review data entered in database and hardcopies of data collection sheet on a regular basis to ensure data integrity. PI will audit the data entered into the database against hardcopies to ensure maintenance of data integrity. Active feedback about data input performance will be given.

### **7.2. Data Entry and Storage**

Raw data will be collected on a standardized data collection sheet. These hardcopy documents will be filed and kept in a locked cabinet. Only study team members have access to cabinet.

Data will be keyed into a password-protected database. Only study team members have access to this database.

## **8. SAMPLE SIZE AND STATISTICAL METHODS**

### **8.1. Determination of Sample Size**

A pilot group of 15 patients will be recruited for this prospective study to investigate the safety and efficacy of HIFU for the treatment of varicose veins.

### **8.2. Statistical and Analytical Plans**

Categorical data will be presented as frequency (percentage). Numeric data will be presented as mean (standard deviation) for parametric distribution and median (interquartile range) for non-parametric distribution.

The primary endpoint of complete closure at different time points will be reported as frequency and percentage (95% CI). Comparisons of the quality of life and functional results at baseline and after treatment at different time points will be examined using pair t-test or Wilcoxon Signed Rank test, where appropriate.

A two tailed, p-value of <0.05 was considered statistically significant. Statistical analysis will be performed with SPSS statistical software, version 19.0 (IBM Corp. Armonk, NY).

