## **2. HYPOTHESIS AND OBJECTIVES**

Primary Objective:

The aim of the study is to evaluate the efficacy of non-invasive echotherapy for the treatment of varicose veins, within local population, using the Sonovein® device. The quality of life scores at baseline, 2 weeks, 3 months, 6 months and 12 months will be assessed using the EQ-50D, AVVQ and CIVIQ scores. Patient satisfaction at these time points will also be assessed.

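### Section 8.2 tests the three Primary Objective scores at four visits at an unadjusted 0.05 with no lead comparison, so the chance of some false positive is about 25% to 40%, not 5%

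*Protocol*

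**What the plan says.** All references are to the protocol.

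- **Section 2** makes efficacy the Primary Objective and measures it by quality of life, which "will be assessed using the EQ-50D, AVVQ and CIVIQ scores" (EQ-50D is evidently EQ-5D). It adds: "Patient satisfaction at these time points will also be assessed".
- **Section 5** fixes the schedule: "Questionnaires will be conducted at 5 timepoints – baseline before procedure, 2 weeks, 3 months, 6 months and 12 months". Its line for the later visits adds a clinical severity score: "follow-up in clinic with VCSS, AVVQ, CIVIQ and EQ-5D".
- **Section 8.2** gives the analysis: "Comparisons of the quality of life and functional results at baseline and after treatment at different time points will be examined using pair t-test", or by the Wilcoxon signed rank test where that is suitable. The decision rule is "A two tailed, p-value of <0.05 was considered statistically significant".
- **Section 8.2** also names complete closure as the primary endpoint, reported as a frequency and percentage with 95% CI. It attaches no test and no single time point to it. Numeric data are summarised by mean (SD) or median (IQR).

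No score or visit is singled out among the before-after comparisons, and no adjustment is stated.

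**The concern.** The before-after comparisons are the only hypothesis tests in the plan, and they fall on the outcomes that section 2 uses to define efficacy. The 0.05 threshold applies to each test separately. With many tests and none designated as leading, the 5% does not describe the chance that the set as a whole produces a significant result by luck. The score and visit to be emphasised can also be chosen after the data are seen.

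The Primary Objective (quality of life) and the primary endpoint (closure) point to different outcomes. The protocol therefore does not settle which result carries the efficacy message, and a report could lean on whichever quality-of-life comparison crossed 0.05. With about 15 patients, the size of the paired change and its uncertainty would tell the reader more than a list of p-values.

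**Working it through.** The protocol states no overall error rate, power or sample-size calculation, so the only figure to start from is the per-test 0.05.

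**Inputs from the protocol**
- Threshold: 0.05, two-sided, per test (section 8.2).
- Scores in the Primary Objective: 3 (section 2).
- Visits compared with baseline: 5 time points − 1 baseline = 4 (section 5).
- Patients: 15 (sections 4.1 and 8.1). Section 5 says 30, so both were tried.

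**Number of tests.** 3 × 4 = 12. Satisfaction is left out because it has no meaningful pre-treatment value. Adding VCSS, which is not in the Primary Objective, gives 4 × 4 = 16.

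**If the tests were independent**
- Any significant result, 12 tests: 1 − 0.95^12 = 0.460.
- Any significant result, 16 tests: 1 − 0.95^16 = 0.560.
- Any significant improvement, 12 tests: each test has 0.05/2 = 0.025 in that direction, so 1 − 0.975^12 = 0.262.

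**Allowing for correlation.** The tests use the same patients and one shared baseline, so they are not independent. The protocol gives no correlations, so those below are assumptions. Paired t-tests were simulated with normal data, n = 15 and no true change on any score at any visit. The correlation between baseline and each visit was 0.5.

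| Between scores | Between later visits | Any of 12 significant | Any of 16 significant |
|---|---|---|---|
| 0 | 0.5 | 0.404 | 0.497 |
| 0.3 | 0.5 | 0.391 | 0.478 |
| 0.5 | 0.5 | 0.363 | 0.443 |
| 0.5 | 0.7 | 0.317 | 0.380 |
| 0.7 | 0.7 | 0.277 | 0.331 |
| 0.7 | 0.8 | 0.246 | 0.289 |

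The 12 tests thus give about 25% to 40%. With n = 30, the 12-test figure is 32% to 40% (between-score correlation 0.7 down to 0, visits 0.5), so the larger sample does not change the picture.

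**False improvement only, 12 tests.** With between-score correlation 0.3 to 0.7, the simulated figure is about 16% to 20%. That is a narrower set of assumptions than the table. Under the null the two directions are equally likely, so the figure is never less than half the two-sided one. At the most correlated row of the table that floor is 0.246/2 = 0.123.

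**After a fix.** One lead comparison has an error rate of 0.05. For comparison, a Bonferroni threshold of 0.05/12 = 0.0042 over all 12 tests gave a simulated overall rate of 0.031 to 0.047.

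**The case against.** The strongest case against has four parts.

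**This belongs in the SAP.** Ordering of comparisons, adjustment and interval reporting are commonly left to a SAP, and none is shown. This stands in part: a SAP could still order or adjust the tests, and the missing interval for the paired change would not be a finding by itself. But the protocol is not silent on the decision rule. It states one without qualification for the only tests it plans, and following it as written gives the rates above.

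**Closure is the primary endpoint, and this is a pilot.** In section 8.2 the quality-of-life tests are not the designated primary analysis. A reader might infer that HIFU would be declared effective as soon as any one test crosses 0.05. The protocol does not say so: no conclusion is tied to any p-value. This stands and lowers the weight of the point. It does not remove it, because section 2 still defines efficacy through these scores, section 8.1 says the pilot is to investigate efficacy, and a purely descriptive pilot would need no significance threshold.

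**Two-sided rates overstate the harm.** Only a false improvement would favour HIFU, and its rate is about half the two-sided one. This stands, and both figures are given.

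**Effect sizes are not absent.** A reader might infer that only p-values will be reported. That is wrong: means (SD) or medians (IQR) are planned, and with complete pairs the difference in means is the mean paired change. What is not planned is an interval for that change.

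**Conclusion.** The point holds at moderate weight. Twelve unadjusted tests on the Primary Objective scores, with no lead, carry a chance of about 25% to 40% of at least one nominally significant result, against the nominal 5%. For a false improvement the chance is about 16% to 20%, against 2.5% for a single test in that direction. The independent-test values, 46% and 26%, are best read as upper figures.

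These rates rest on the assumed correlations, on paired t-tests with complete normal data, and on no score truly changing at any visit. If some scores do change, the rate applies only to those that do not.

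A reader might infer that a chance positive on the Primary Objective is close to a coin flip. The protocol does not support that. For the 12 tests it would need independence, which the shared patients and baseline rule out. Figures near 50% otherwise appear only when scores outside the Primary Objective are added.

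**What to change.** In section 8.2:

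1. Name in advance one quality-of-life score at one visit, for example AVVQ at 12 months versus baseline, as the only quality-of-life comparison tested at 0.05.
2. Report every other score-by-visit comparison as an exploratory paired mean or median change with 95% CI, with no significance claim.
3. State how this comparison relates to complete closure, so that sections 2 and 8.2 agree on which result carries the efficacy conclusion.

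If more than one significance claim is wanted, list those comparisons in advance and apply Holm across them.

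The cost is a few sentences, with no new data or patients. The downside is that fewer results can be called significant.
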